5.2.7. Follow-up Visits - Midterm/ Days 35-49 and Long Term/ Days 77-91

The following procedures and assessments will be performed and documented:

- Lower limb volume (for each knee) by measuring lower limb circumferences
- KSKSS (for each knee)
- Range of Motion (for each knee)
- Scar cosmesis assessment (for each knee)
- Straight leg raises (for each leg)
- SSC assessment (for each knee)
- Concomitant Medications
- AE assessment and SAE reporting
- Health Economics assessments
- End of Study, after long term follow-up

5.2.8. *Unscheduled Visits*

Outside of scheduled study visits, if the subject needs to be assessed by the investigator for any reason related to either knee, the following procedures and assessments will be performed and documented in the subject's medical records/source notes:

- Lower limb volume (for each knee) by measuring lower limb circumferences
- KSKSS (for each knee)
- Range of Motion (for each knee)
- Scar cosmesis assessment (for each knee)
- Straight leg raises (for each leg)
- SSC assessment (for each knee)
- Pain assessment
- Concomitant medications
- AE assessment and SAE reporting
- Health Economics
- End of study, if a subject is withdrawn early

6. RISKS ASSOCIATED WITH STUDY PARTICIPATION

Participation in the clinical investigation presents low risks to subjects. Some risks are generalized and are listed below:

Risks	Disorders/Conditions
Skin and Subcutaneous Tissue	
 • Epidermal (skin) stripping • Contusion (bruising) • Maceration • Minor soft tissue damage • Local cutaneous reaction (i.e., redness, rash, significant pruritis, urticaria) • Minor bleeding • Pain
Other	
 • Bleeding complications (associated with the surgical procedure, concomitant therapy, and co-morbidities) • Localized infection • Exposure related infection • First-degree burn (if the device gets warm) • Minor desiccation (due to dressing leak) • Moderate soft tissue damage (i.e., due to trip hazard, tubing entanglement) • Deterioration of the wound (due to lack of visibility of incision site through dressing) • Physical discomfort

7. SAFETY AND ADVERSE EVENTS

7.1. Definitions

7.1.1. Adverse Event (AE)

Any untoward medical occurrence, unintended disease or injury, or untoward clinical signs (including clinically significant abnormal laboratory findings) in subjects, users or other persons, whether or not related to the investigational medical device.

7.1.2. Serious Adverse Event (SAE)

[figure not shown]
An AE is considered serious if it results in any of the following outcomes:

- Death
- Life-threatening
- Hospitalization (initial or prolonged)
- Persistent or significant incapacity or substantial disruption of the ability to conduct normal life functions
- Congenital anomaly/birth defect
- Required intervention to prevent permanent impairment or damage
- Other important medical events may be considered serious when, based upon appropriate medical judgment, they may jeopardize the subject and may require medical or surgical intervention to prevent one of the outcomes listed in this definition.

Any planned hospitalization for a pre-existing condition, or a procedure required by the protocol, without serious deterioration in health, is not considered an SAE.

7.2. Classification

7.2.1. Relationship to Study Treatment

The investigator will assess the relationship of the AE as:

- **Related** to the study product: any AE for which there is a reasonable possibility that the study product caused the AE. The sponsor will review all SAEs for expectedness.
- **Not Related** to the study product: when it is determined that there is no relationship between the AE and the use of the study product.

7.2.2. Severity

The investigator will assign severity as:

- **Mild** – asymptomatic or mild symptoms; clinical or diagnostic observations only; no intervention indicated
- **Moderate** – minimal, local, or non-invasive intervention indicated
- **Severe** – medically significant but not immediately life-threatening; hospitalization or prolongation of hospitalization indicated; disabling

7.3. AE Reporting Procedures

The investigator is responsible for monitoring the safety of all subjects enrolled in the study and reporting AEs as described in this protocol.

7.4. AE Collection/Reporting Period

The AE collection/reporting period will begin after the subject has been randomized. Investigators should assess for AEs at each visit. In addition, study subjects should be instructed to report any AE that they experience to the investigator.

All AEs, regardless of perceived relationship to study product, will be reported and documented in a timely manner. In addition, the worsening of a medical condition previously reported in the medical history should also be recorded as an AE.

The AE description will include the nature of the experience (AE term), the start date, the end date, the severity of each sign or symptom, the seriousness of the event or experience, relationship to study treatment, the course of action taken, and the outcome of the experience. It will be indicated if the AE caused the subject to be discontinued from the study.

7.5. SAE Reporting to Sponsor

The SAE collection/reporting period will begin after the subject has been randomized. SAEs will be reported via the sponsor's SAE Report Form. This form should be completed by the investigator, or designee, and submitted (fax or email) to the sponsor within 24 hours of the investigator becoming aware of the event. The sponsor's SAE e-mail inbox is available for SAE reporting 24 hours per day and is monitored during normal business hours.

7.6. UADE Reporting - Unanticipated Adverse Device Effect (UADE)

A UADE is any SAE on health or safety or any life-threatening problem or death caused by, or associated with, a device, if that effect, problem, or death was not previously identified in nature, severity, or degree of incidence in the investigational plan or application (including a supplementary plan or application), or any other unanticipated

serious problem associated with a device that relates to the rights, safety, or welfare of subjects.

The sponsor will immediately conduct an evaluation of the received SAEs to determine whether the event meets the UADE definition. If the event is determined to be a UADE, sponsor will report the results of the evaluation to all regulatory agencies overseeing the project and to participating investigators.

If the sponsor determines that the event presents an unreasonable risk to the study subjects, the sponsor will terminate all clinical studies or parts of studies presenting risk as soon as possible.

7.7. Follow-up Period for Ongoing AEs

Treatment-related AEs (serious and non-serious) that are ongoing at the final study visit will be followed up to 30 days to assess resolution or stabilization. All unrelated AEs will be considered closed at the time the subject completes participation in the study.

8. STATISTICAL CONSIDERATIONS

8.1. Analysis Sets

The following analysis sets will be used:

- Intention-to-treat (ITT) Analysis Set – The ITT Set will consist of all randomized subjects. Subjects/Knees will be analyzed according to the treatment allocated at randomization for that particular knee (right or left)
 - In the event each treatment is allocated to a knee different than what they were randomized to, the subject/knee will be counted under the treatment received as long as the subjects receives each treatment once (one treatment per knee).
 - In the event subjects receive the same treatment in both knees, each knee will be counted once in each unique treatment group according to the

treatment allocated as per the randomization and will not be counted twice under the same treatment group.

- Per-Protocol (PP) Analysis Set – The PP Set will include all subjects and/or knees in the ITT Analysis Set with no disqualifying protocol deviation(s) that would impact the interpretation of the primary endpoint. The disqualifying protocol deviation(s) for exclusion from this set will be defined and documented prior to the final database lock.
- Safety Analysis Set – The Safety Analysis Set will consist of all subjects and/or knees that received any on study treatment-related procedures. Subjects/Knees will be analyzed according to the treatment received in each knee.

8.2. Planned Analysis and Data Summaries

8.2.1. General Analysis Techniques

In general, summaries of endpoints will consist of descriptive statistics. Data will be summarized by treatment group, overall and/or by visit, if applicable. Due to each subject serving as their own control and receiving both treatments (one treatment per knee), the same subjects will be counted once within each treatment group according to the treatment received and/or randomized in for each knee. Subjects who only have one knee treated will only be counted in the treatment group that the knee received. Data processing, tabulation of descriptive statistics, and any graphical representations will be performed primarily using SAS (release 9.4 or higher). If the use of other software is warranted, details will be included in the clinical study report (CSR).

Summaries of continuous variables will display the number of subjects and/or knees with available data (n), the mean, median, standard deviation, minimum, and maximum values at each time point. For categorical variables, the number and percentage of subjects and/or knees that are in each category will be provided. The denominator for percentages will be all relevant subjects and/or knees in a particular analysis, including those for whom data are not reported or missing.

Formal statistical testing will be conducted utilizing two-sided tests at a significance level of 0.05. Corresponding 95% confidence intervals (CIs) will be presented for appropriate endpoints.

Additional analyses to characterize the safety and/or efficacy may be conducted. These additional analyses will be included in the Statistical Analysis Plan. Any ad hoc summaries/analyses conducted after database lock will be included in the CSR and labeled as *ad hoc*.

8.2.2. Subject Disposition

Summaries of disposition will be tabulated by treatment group and overall. At a minimum, the following summaries containing the number of subjects and percentage of subjects will be included for subjects:

- Included each analysis set
- Provided informed consent
- Randomized and treated
- Discontinued early from the study for any reason, along with the reason for discontinuation (if the reason is an AE, the system organ class and preferred term)
- Completed the study as planned

Subject disposition also will be described in a flowchart (CONSORT diagram).

8.2.3. Demographic and Baseline Characteristics

Demographic characteristics (eg, age, sex, race, and ethnicity), baseline characteristics, and other disease characteristics may be summarized by treatment arm and overall.

8.2.4. Analysis of Primary Endpoint

The primary endpoint is the percent change in lower limb volume, as calculated based on manual circumference measurements, 5-7 days after total knee arthroplasty (TKA) when using the PREVENA RESTOR ARTHRO•FORM™ Incision Management System

compared to the control. The lower limb volume is calculated using the Frustum formula^{35;36}:

$$Volume = \sum \pi(x_{(i+1)}^2 + x_i^2 + x_i \cdot x_{(i+1)}) \left(\frac{h}{3}\right)$$

where x_i and x_{i+1} are the circumferences of two consecutive sections along the limb, and h is the length of the interval between the two measurements on the limb. The lower limb volume is determined by calculating the sum of the volumes of all sections. The percent change of the lower limb volume is defined as the difference of lower limb volume from baseline (pre-op) to postoperative Day 5-7, divided by the baseline measurement of lower limb volume, multiplied by 100.

A general linear mixed model repeated measures analysis (MMRM) will be used to analyze the primary endpoint with covariates: site, study visit, treatment, knee side (left/right), baseline lower limb volume, baseline BMI category ($<30 \text{ kg/m}^2$, $\geq 30 \text{ kg/m}^2$), and treatment by study visit. Knee side will serve as a repeated-measure factor to account for the correlations between left knee and right knee on the same subject, and the subject variable will also be specified to identify those observations that are to be correlated. Raw means, LS Means, including 95% confidence intervals, will be presented by treatment group. The ITT analysis set will be used for the primary analysis.

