4.9. Lower Limb Volume

Lower limb volume for each leg will be calculated using two different methods. The first will be the Partial Frustum Model method³¹, using measurements of circumference taken above and below the patella. The circumferences of each limb will be measured at the center of the patella, every 5 cm from the center of the patella to 15 cm superior to the patella (ie, 3 measurements), every 5 cm from the center of the patella to 20-30 cm inferior to the patella (ie, no less than 4 but no more than 6 measurements). Additionally, the circumference 1 cm above the superior edge of the medial malleolus will also be measured for each leg; however, the measurement taken 1 cm above the malleolus should not overlap with the most inferior measurement taken below the patella. There will be a total of nine (9) to 11 measurements per leg. The volume of each leg segment (between two measures of circumference) will then be calculated using a formula for a

truncated cone, and the sum of all segments will then be calculated to determine lower limb volume.

The second method for calculating lower limb volume will utilize a mobile 3D imaging system (LymphaTech) that combines an infrared depth sensor with a tablet computer using proprietary software. 3D imaging will be performed by the investigator or investigator designee according to the User Guide documentation that accompanies the tablet computer that is provided to the investigators. Briefly, the subject will stand with their feet shoulder-width apart on a flat surface with an approximately 1 meter radius of free space on all sides. The investigator will then scan both legs by slowly walking around the subject while keeping the camera pointed at the subject and moving the camera up and down to capture a 3D rendering (ie, image) of the entirety of both legs. During the scan, the subject should remain as still as possible, and the lower limbs should be free of any materials that will distort the image (eg, clothing covering the area). Once the 3D rendering is obtained and inspected for quality, lower limb volume will be calculated using scan measurements from the mid-thigh to the ankle of each leg, excluding the gluteal fold region of each leg, the heel/ankle region of each leg, and the feet.

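### Section 8.2.4 puts circumferences into the radius form of the frustum formula, so absolute manual limb volumes come out 39.48 times too large; percent-change endpoints are unaffected

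*Combined protocol and SAP*

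**What the plan says.** Section 4.9 (Lower Limb Volume) describes two ways of obtaining volume. The manual one works by "using measurements of circumference taken above and below the patella", with nine to 11 circumferences per leg. Each stretch between neighbouring measurements is to be treated as a truncated cone, and the pieces are then added up: "and the sum of all segments will then be calculated to determine lower limb volume". The section prints no formula. For the other method it says: "The second method for calculating lower limb volume will utilize a mobile 3D imaging system" with proprietary software.

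Section 8.2.4 (Analysis of Primary Endpoint) prints the formula for the manual volume, Σ π(x₁² + x₂² + x₁x₂)(h/3). It defines the two x values by saying that they "are the circumferences of two consecutive sections along the limb" and h by saying that it "is the length of the interval between the two measurements on the limb". The endpoint is the change in volume from the pre-operative baseline to Day 5-7, "divided by the baseline measurement of lower limb volume, multiplied by 100". Absolute volume also enters the primary model, whose covariate list includes "baseline lower limb volume, baseline BMI category". The sensitivity model in 8.2.4.1 adjusts for baseline volume as well.

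**The concern.** The volume of a truncated cone with end radii r₁ and r₂ and height h is (πh/3)(r₁² + r₂² + r₁r₂). Section 8.2.4 has exactly this form, but its inputs are circumferences. A circumference is 2π times a radius and every term is of second order, so the expression does not return a limb volume.

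This is the defining formula of the primary endpoint. A programmer who follows it literally fills the analysis data set with impossible leg volumes. One who quietly corrects it departs from the protocol, and section 8.6 asks for changes from the planned analyses to be noted in the clinical study report. At stake are the absolute manual volumes that may be tabulated. Section 8.2.5 provides for raw means and changes from baseline where appropriate, and section 8.2.3 allows a summary of baseline characteristics. The baseline-volume coefficient would also be on a wrong scale.

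**Working it through.** **Inputs.** The formula and the definitions of x, h and percent change come from 8.2.4, the measurement sites from 4.9, and the planning figures from 8.3.1. The protocol states no numerical limb volume, so no volume can be reproduced.

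**The plan's own figure.** The sample size is stated in percent-change units: 13.6% against 8%, a difference of 5.6 points, with SD 9.2, two-sided α 0.05 and power 0.80. A two-sample t-test needs 43.35, hence 44 per arm. Each subject gives one knee to each arm, and 44/(1 − 0.15) = 51.8, so 52 subjects. This reproduces the stated 52. No absolute volume enters the calculation.

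**Size of the error.** Put r = C/(2π) into the frustum formula:

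- correct: (πh/3) × (C₁² + C₂² + C₁C₂)/(4π²) = (h/(12π)) × (C₁² + C₂² + C₁C₂), multiplier 1/(12π) = 0.02653
- as printed: (πh/3) × (C₁² + C₂² + C₁C₂), multiplier π/3 = 1.0472
- ratio: (π/3)/(1/(12π)) = 12π²/3 = 4π² = 39.478

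The ratio does not depend on C or h. It is the same for every segment and so for every sum.

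**Illustration on an assumed leg.** These circumferences are my assumption. They follow the nine-site layout of 4.9, from 15 cm above the patella to 20 cm below it, then the ankle: 50, 47, 44, 40, 37, 38, 36, 30 and 23 cm, with seven intervals of 5 cm and one of 12 cm (47 cm in all).

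- Σ h(C₁² + C₂² + C₁C₂) = 198,528
- as printed: 198,528 × π/3 = 207,898 cm³, about 208 L
- corrected: 198,528/(12π) = 5,266 cm³, about 5.3 L

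**Percent change.** Assume that the same circumferences rise by 5, 7, 9, 10, 7, 6, 5, 4 and 3% after surgery.

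- as printed: 236,434/207,898 − 1 = 13.73%
- corrected: 5,988.9/5,266.1 − 1 = 13.73%

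In general (kV₁ − kV₀)/(kV₀) = (V₁ − V₀)/V₀ for any constant k. The cancellation therefore also holds for the secondary volume endpoints at visits 4, 5 and 6.

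**Model.** Multiplying a linear covariate by k divides its slope by k and leaves the fitted values alone. As a numerical check, one simulated paired data set (44 subjects, random subject intercept, treatment, knee side, baseline volume) was fitted with baseline volume on each scale. The treatment estimate (−8.052), its standard error (1.456) and the p-value (3.2 × 10⁻⁸) were the same both times. The baseline-volume slope went from −3.198 to −0.0810, a ratio of 39.48. These values describe that one simulated set only; the point is that they do not move.

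**Where the cancellation needs care.** It requires one formula at both visits. With a true change of +13.6%, a baseline computed as printed and a follow-up computed correctly give 1.136/39.478 − 1 = −97.1%. The reverse gives 1.136 × 39.478 − 1 = +4,385%.

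**The case against.** The strongest reply is that nothing planned for inference changes. The primary endpoint and the secondary manual-volume endpoints are percent changes, the circumference endpoints do not use volume, and the treatment effect is invariant to the scale of the covariate. All of that stands.

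It can also be said that the intent is clear. Section 4.9 asks for a truncated cone built from circumferences, and 8.2.4 names the frustum method with citations, so this is a slip of notation. That is fair. Section 4.9 is evidence of what was meant and not a second place where the error occurs. But it supplies no formula and no conversion to radius, so it does not repair 8.2.4. Section 8.6 defers full analysis details to a separate SAP whose text is not in the document reviewed. What will actually be programmed is therefore unknown.

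Thirdly, a leg of about 200 L would be caught at the first listing. That is likely, but it is a reason to correct the formula beforehand rather than to leave it.

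Finally, absolute volumes are not firmly promised. The raw means in 8.2.4 refer to the percent change, 8.2.5 is qualified by appropriateness, and 8.2.3 is optional and does not name limb volume. This stands too: the harm is to absolute manual volumes if they are reported.

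**Conclusion.** Wrong as written, low impact. Taken literally, 8.2.4 inflates every volume derived from manual circumferences by exactly 4π² = 39.48. This rests only on geometry and on the protocol's own definition of x; the sources cited for the formula were not available. The litre figures depend on the assumed leg, but the factor does not.

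A reader might infer more, and the documents do not support it:

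- **That the primary result is biased, or the trial mis-sized.** The constant cancels in percent change, the covariate slope absorbs it in the model, and the 52 subjects come from percent-change assumptions.
- **That every limb volume in the trial is wrong.** The 3D volumes come from separate software and do not use this formula.
- **That a planned comparison of manual with 3D volumes will fail.** None is planned, and the 3D endpoint is itself a percent change. The two methods also cover differently defined regions of the leg, so absolute agreement would not be assured even with a correct formula.

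What remains is any absolute manual volume shown under 8.2.5, a baseline-volume summary if one is produced, and the scale of the baseline-volume coefficient in the primary and sensitivity models.

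**What to change.** In 8.2.4, write Volume = Σ (h/(12π))(C₁² + C₂² + C₁C₂), with C₁ and C₂ the consecutive circumferences and h the length of that segment. Alternatively, keep the printed expression and define x as the radius, C/(2π). Carry the same formula into the SAP and use it at baseline and at every later visit. Section 4.9 needs no change.

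If the protocol text is not amended, put the corrected formula in the SAP before database lock and note the change in the clinical study report, as 8.6 provides. The cost is one line of text and one line of code, with no effect on design, sample size, measurements or conduct.

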8.2.4.1. Sensitivity Analyses of Primary endpoint

- The primary analysis will be repeated on the Per-Protocol analysis set.
- The primary analysis will be repeated on the ITT analysis set to explore the following covariate: treatment, site, visit, baseline lower limb volume, surgical approach, and length of incisions.
- Additional sensitivity analyses may be conducted to explore other characteristics that may impact the lower limb volume. All analyses will be outlined in the Statistical Analysis Plan.

8.2.5. Analysis of Secondary Endpoints

All secondary endpoints will be summarized by treatment group on the ITT population. Raw means and changes from baseline will be displayed by treatment group, as appropriate.

The following continuous endpoints:

- Percent change in lower limb volume, as calculated based on manual circumference measurements, from baseline to visits 4, 5, and 6
- Percent change in circumferences from baseline to visits 3-6 that are measured at:
 - 10 cm above the center of the patella
 - at the center of the patella
 - 10 cm below the center of the patella
 - at the ankle; 1 cm above the medial malleolus
- Change of knee flexion angle from baseline to visits 3-6
- Change of knee extension angle from baseline to visits 3-6

Change of total ROM degrees, defined as the flexion angle minus the extension angle, from baseline to visits 3-6 will be analyzed using a mixed model repeated measures analysis (MMRM) with the same covariates outlined in the primary analysis. General linear mixed models and/or paired t-tests at each week may also be performed.

The average pain and worst pain in each leg in the last 24 hours using an NPRS (numerical pain rating scale) of 0-10 (daily for 4 weeks post-surgery, then weekly for weeks 5-12) will be analyzed in the following two ways:

- An AUC, or area under the receiver operating characteristics (ROC) curve, will be calculated for daily pain scores for each knee using a general linear mixed model with site, treatment, and knee side (left/right) included in the model as

covariates while adjusting for correlations from the within-subject comparisons over time. A model with an AUC of at least 0.70 will be considered adequate.³⁷

- Weekly pain scores (average pain scores for each week (weeks 1-4) and reported weekly pain scores (weeks 5-12)) will be analyzed using an MMRM with site, week, treatment, knee side (left/right), and treatment by week included in the model as covariates while adjusting for correlations from the within-subject comparisons over time. The covariance structure will be selected based on the lowest Akaike Information Criterion value. Raw means, LS Means, including 95% confidence intervals, will be presented by treatment group.

A Chi-square, McNemar's, or Fisher's test as appropriate will be used to analyze the following endpoints:

- The incidence of SSCs by visits 5 and 6
- Scar cosmesis assessment at visits 3-6

Additional details will be specified in the Statistical Analysis Plan.

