4.10. Knee Range of Motion

ROM is the full movement of the joint, measured as an increased or decreased angle (ie, degrees) between the bones of the limb at the joint. ROM for the knee includes flexion (bending) and extension (straightening). A completely straight knee will have a joint measure of 0° while a fully bent knee (without crouching) will have about 135° of flexion. For this study, the flexion and extension angles of each knee will be captured using a goniometer with the subject lying flat, in the supine position. ROM will be calculated as the difference between the flexion angle and the extension angle. Both active ROM, whereby the subject flexes and extends the joint without assistance, and passive ROM, whereby the investigator or investigator designee flexes and extends the joint, will be captured.

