4.12. Pain Assessments

Pain will be captured daily for the first 4 weeks post-surgery and then weekly for weeks 5-12. In addition, a baseline pain assessment associated with each knee will be captured at screening and recorded by the investigator or investigator designee. After surgery, the pain associated with each leg will be electronically recorded using an ePRO system as part of the EDC. Subjects will receive reminders (eg, phone calls, e-mails, or ePRO system reminders) to log-in by computer or use an app to complete their pain assessments.

For all pain assessments, subjects will evaluate their average pain and their worst pain associated with each leg for the previous 24hr period using the numerical pain rating scale (NPRS), which ranges from 0 (no pain) to 10 (extremely painful).

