8.3.2. Randomization

All subjects who meet all inclusion criteria and no exclusion criteria will be randomized in a 1:1 ratio to receive the PREVENA RESTOR ARTHRO•FORM™ Incision Management System or the control in either right or left knee. Each subject will receive both treatments (one treatment per knee). A randomization schedule, including randomization numbers and treatment assignments, will be generated and maintained centrally in the web-based clinical database management system. Once randomized, a subject's assignment cannot be altered or changed; a subject should not be randomized twice. The randomization schedule will be kept blind to any person who is involved in the daily operations of the study. It will only be accessible to the study biostatisticians who generate and review the schedule, and the vendor's team members (if an EDC vendor is utilized) who are involved in reviewing the schedule and uploading the schedule.

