8.6. Statistical Analysis Plan and Changes in Analyses

A Statistical Analysis Plan (SAP) containing full details of the statistical analyses and execution will be prepared for this study. The SAP (SAP) will be finalized prior to locking

the study database and the final analysis. Any changes from the planned analyses in this protocol or SAP will be noted in the Clinical Study Report (CSR).

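### The total-ROM change model adjusts for baseline limb volume but not for that knee's baseline ROM, and the weekly pain MMRM has no baseline pain term: possible loss of precision on secondary endpoints, no bias

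*Combined protocol and SAP*

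**What the plan says.** Section 8.2.4 lists the covariates of the primary model for percent change in limb volume: "site, study visit, treatment, knee side (left/right), baseline lower limb volume, baseline BMI category", plus treatment by study visit. Limb volume is the only outcome whose baseline appears there.

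Section 8.2.5 takes that list over for change in total ROM, which "will be analyzed using a mixed model repeated measures analysis (MMRM) with the same covariates outlined in the primary analysis". Limb volume, circumference, flexion and extension are listed just above, but their sentence has no verb. That the same model covers them is an inference.

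For pain, section 8.2.5 says that weekly scores "will be analyzed using an MMRM with site, week, treatment, knee side (left/right), and treatment by week included in the model as covariates". The response is the score itself, not its change from baseline, and no baseline pain term is named.

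The baselines exist. Section 5.2.2 has ROM measured on each knee before surgery. Section 4.10 records two kinds: "Both active ROM, whereby the subject flexes and extends the joint without assistance, and passive ROM". Section 4.12 says that "a baseline pain assessment associated with each knee will be captured at screening", whereas sections 5.1 and 5.2.2 place that assessment pre-operatively on Day 0. Under either timing it precedes randomization, which section 4.8 sets at closure of the first knee.

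**The concern.** In a design with one knee per arm, site and BMI category are the same for both knees of a subject. As main effects they do little for the between-knee contrast. A covariate that differs between the knees is what can sharpen it. The ROM model has one such baseline covariate, but it belongs to a different outcome. The weekly pain model has none.

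At stake is the width of the confidence intervals for the treatment effect on ROM and on weekly pain. Any chance imbalance in baseline ROM or pain between the two arms is part of that same imprecision, not an extra harm.

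**Working it through.** **The plan's own figure.** Section 8.3.1 assumes means of 13.6% and 8% (difference 5.6), SD 9.2, two-sided alpha 0.05, 80% power and a two-sample t-test. This gives 43.35, so 44 per arm; 44/0.85 = 51.8, so 52 subjects, each supplying one knee per arm. The stated 52 reproduces. It concerns limb volume only, and no power is stated for ROM or pain. The illustration below uses 52 × 0.85 = 44 pairs.

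**Assumed inputs.** The documents give neither of the following, so both are varied:
- r: correlation between baseline and follow-up of the between-knee difference;
- k: follow-up SD divided by baseline SD of that difference.

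**ROM.** In units of the baseline variance of the between-knee difference, the change score has variance 1 + k² − 2rk, and the follow-up adjusted for baseline has variance k²(1 − r²). The ratio, adjusted to unadjusted, is k²(1 − r²)/(1 + k² − 2rk). No degree of freedom is charged, because one covariate replaces another.

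| k | r = 0.3 | r = 0.5 | r = 0.7 |
|---|---|---|---|
| 1 | 0.65 | 0.75 | 0.85 |
| 1.5 | 0.87 | 0.96 | 1.00 |
| 2 | 0.96 | 1.00 | 0.93 |

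At k = 1 the confidence interval is multiplied by the square root of the ratio: 0.81, 0.87 and 0.92. A change score fixes the baseline slope at 1, while the best slope is rk. The gain therefore vanishes where r = 1/k (r = 0.67 at k = 1.5; r = 0.5 at k = 2). Values of k below 1 would enlarge the gain.

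**Weekly pain.** The score is modelled directly, so the ratio is (1 − r²), times 1 + 1/(44 − 3) = 1.024 for the added coefficient.

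| r | 0 | 0.1 | 0.3 | 0.5 | 0.7 |
|---|---|---|---|---|---|
| variance ratio | 1.02 | 1.01 | 0.93 | 0.77 | 0.52 |

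At r = 0.3, 0.5 and 0.7 the interval is multiplied by 0.97, 0.88 and 0.72. Break-even is at r = √(1 − 1/1.024) = 0.15.

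**Check by simulation.** With 20,000 trials of 44 pairs, the left-right difference was regressed on side, treatment and a baseline. Baseline volume was assumed unrelated to ROM.
- Swapping baseline volume for baseline ROM gave 0.66, 0.76 and 0.86 at k = 1 for r = 0.3, 0.5 and 0.7.
- Adding baseline pain gave 0.93, 0.78 and 0.52.
- Mean estimates stayed within 0.002 SD of zero with and without the term.

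A separate simulation of paired knees gave ROM ratios at k = 1 of 0.65 to 0.87.

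**Pooled slope.** The formulas use the within-subject slope. A knee-level baseline entered once in the MMRM has a single slope that mixes within- and between-subject relations. Where the two slopes match, the ratios above hold to within about 0.03. Where they differ, the result is less favourable:
- Weekly pain, with an assumed between-subject slope of 0.6 and knees correlated 0.3 to 0.7 at baseline: about 1.09 to 1.11 at r = 0.1 and 1.01 to 1.04 at r = 0.2. Other unequal slopes gave up to about 1.12 at r = 0.
- ROM: up to about 1.14 at k = 1.5, r = 0.7, close to r = 1/k.

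With a pooled slope, break-even for pain is therefore roughly r = 0.15 to 0.25, not a firm 0.15.

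**The case against.** The strongest reply is that this is a modelling preference. Change-score analysis of randomized within-subject data is valid, the endpoints are secondary in a pilot, and the size of the loss cannot be determined from the documents. That stands as a limit on severity. It does not remove the gain available from data already collected.

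A second reply is deferral. Section 8.2.5 ends by saying "Additional details will be specified in the Statistical Analysis Plan", and it also allows other mixed models or paired t-tests. The SAP may well add the terms. But the protocol is not silent here: it names the covariates, and section 8.6 states "Any changes from the planned analyses in this protocol or SAP will be noted in the Clinical Study Report". Correcting the text now avoids having to report a departure.

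A third reply is that the same covariates could be read by role, so that baseline volume becomes baseline ROM. The literal text is against this, since section 8.2.4 names limb volume. The reading does show that the sentence needs clarifying.

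The sizing also has limits. It models one visit, while the plan is an MMRM over several visits or weeks. The swap simulation assumes that volume says nothing about ROM, which favours the swap. The pooled-slope objection holds and is built into the figures above.

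A reader might infer that the treatment estimates for ROM or pain are biased. The documents do not support this: side is randomized within subject after the baseline assessments (sections 4.8 and 8.3.2), and withdrawal takes both knees together (section 4.4.2).

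**Conclusion.** The point holds as a minor one. As written, the total-ROM model carries another outcome's baseline and the weekly pain model carries none, although the right baselines are collected on each knee. The consequence is a possible loss of precision.

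The gain from adjustment is illustrative: at one visit, 44 pairs and k = 1, a variance ratio of about 0.65 to 0.87 for ROM and 0.93 to 0.52 for weekly pain over r = 0.3 to 0.7. It rests on assumed r and k. It can be nil for ROM near r = 1/k and for pain at low r. With a single pooled slope, variance can rise by roughly 10% in those regions.

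Three further inferences are not supported:
- That N = 52 or the primary analysis is weakened. The primary model already contains its own baseline.
- That flexion, extension and circumference are certainly affected. Their sentence is incomplete. Percent change in circumference is also already scaled by its baseline, so any gain there is probably small.
- That the daily pain analysis shares the fault. Its AUC is described as an area under an ROC curve, so its response is undefined and no claim can be made.

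**What to change.** In section 8.2.5:

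1. Complete the sentence for the listed continuous endpoints.
2. For total ROM, and for flexion and extension once their model is stated, use the primary-analysis covariates with baseline limb volume replaced by that knee's baseline value of the endpoint analysed, active with active and passive with passive. Circumference is optional.
3. Add that knee's matching baseline NPRS to the weekly pain MMRM (average with average, worst with worst), after reconciling section 4.12 with sections 5.1 and 5.2.2 on when baseline pain is taken.
4. Preferably enter each baseline as the subject mean plus the knee's deviation from it, so that the within-subject slope is estimated separately from the between-subject slope.

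Cost: a few sentences and no new data. For ROM the swap uses no extra degree of freedom but gives up whatever baseline volume predicts about ROM change. For pain, the within-subject term costs about 2.4% in variance at 44 pairs if baseline pain proves uninformative. Splitting a baseline into mean and deviation adds one further subject-level coefficient. Missing baselines need the usual handling.
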